6.1 Pharmacokinetic Assessments

Time points for collection of blood samples for analysis of study drug (CT-P10, Rituxan or MabThera) concentration are detailed in Section 6.6.1.

Details of blood sampling schemes are provided in Table 7 for patients who receive both courses of treatment in the Main Study Period and Table 8 for patients who receive only first course of treatment in the Main Study Period, respectively.

The total number of samples for analysis of study drug concentration in Part 1 will be 21 samples per patient if the patient receives both first and second courses of treatment and 15 samples per patient if the patient receives only first course of treatment.

The total number of samples for analysis of study drug concentration in Part 2 will be 13 samples per patient if the patient receives both first and second courses of treatment and 7 samples per patient if the patient receives only first course of treatment.

Samples can be obtained via an indwelling venous cannula and heparin lock or saline lock from the arm not receiving the study drug infusion, at the investigator's discretion.

Actual sampling times for each patient will be recorded in the patient's eCRF and individual source documents. See Section 6.6.1 for further information on sample collection for PK analysis.

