- 17. Additional vital signs including blood pressure, heart and respiratory rates, and temperature (before administration [within 15 minutes prior to the beginning of the study drug infusion], within 15 minutes after the end of the study drug infusion, and at 1 hour (±15 minutes) after the end of the study drug infusion) will be assessed to monitor for possible hypersensitivity reactions. In addition, hypersensitivity should be monitored by routine continuous clinical monitoring including 12-lead ECG monitoring 1 hour (±15 minutes) after the end of the study drug infusion. Emergency equipment, such as adrenaline, antihistamines, corticosteroids, and respiratory support including inhalational therapy, oxygen, and artificial ventilator must be available.
- 18. Pharmacokinetic samples will be collected within 15 minutes prior to the beginning of the study drug infusion, within 15 minutes after the end of study drug infusion, and 1 hour (±15 minutes) after the end of study drug infusion on the day of each study drug infusion. For patients from Part 1, additional samples will be collected after 24 hours (±2 hours) from the start of each study drug infusion in the first treatment course and on Days 7, 21, 28, 56, 84 and 112. Testing will be performed at the central laboratory.
- 19. Pharmacokinetic sampling should be done at EOS Visit if the last visit occurs before Week 48.
- 20. B-cell kinetic samples will be collected in the each treatment course within 15 minutes prior to the beginning of the first study drug infusion, within 15 minutes after the end of first study drug infusion and 1 hour (±15 minutes) after the end of first study drug infusion. For patients from Part 1, additional sample will be collected after 24 hours from the start of the first study drug infusion in the first course of treatment.
- 21. Before dosing on Day 0 of Week 0 (after randomization only). Only for patients who sign a separate informed consent form for the biomarker study (genotypes). Blood samples will be evaluated for FcγR genotype (FcγRIIa, IIIa, and/or any necessary genotypes). Testing will be performed at the central laboratory.
- 22. Use of all concomitant medications, from within 30 days of randomization until the last assessment date or End of Study Visit, will be recorded in the patient's eCRF.

Protocol Version 5.1, including Country-Specific Protocol Amendment 1 (US) - 01 April 2016

Protocol Number CT-P10 3.2

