**Table 1: Populations and Subsets of Analysis**

Populations	Subsets
Main Study Period: Part 1	
all-randomized	
safety	
pharmacokinetic	pharmacokinetic (antibody negative subset) pharmacokinetic (antibody positive subset)
Main Study Period: Part 2	
all-randomized	all-randomized (antibody negative subset)
safety	safety – 2 nd treatment course in Main Study Period subset
efficacy	efficacy (antibody negative subset) efficacy (antibody positive subset) efficacy – 2 nd treatment course in Main Study Period subset
pharmacokinetic	pharmacokinetic (antibody negative subset) pharmacokinetic (antibody positive subset) pharmacokinetic – 2 nd treatment course in Main Study Period subset
pharmacodynamic	pharmacodynamic (antibody negative subset) pharmacodynamic – 2 nd treatment course in Main Study Period subset
Extension Study Period	
all-randomized	all-randomized – Extension Study Period subset
safety	safety – Extension Study Period subset
efficacy	efficacy – Extension Study Period subset
pharmacodynamic	pharmacodynamic – Extension Study Period subset

All-randomized, safety and PK populations and its subsets will be defined for the patients from Part 1 and 2, respectively. Efficacy and PD population and its subsets will be defined for the Part 2. Population for Part 2 will include patients from Part 1.

Patients who have any major protocol deviations (as defined in [Section 5.6](#)) may be excluded only from the population (PD and/or Efficacy) that would be affected by the deviation. Patients from the significant GCP non-compliance sites as defined in [Section 5.6](#) will be excluded in all populations.

The number of patients in all populations will be tabulated by the treatment group in each relevant Part and study period. A listing will also be produced, displaying this data.

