### **5.7. Display of Data by Treatment**

All analysis result of Main Study Period excluding ANCOVA will be displayed by the following groups: CT-P10, Rituxan, MabThera, and combined Rituxan and MabThera group.

Analysis of the general and PK section in Main Study Period will be conducted in Part 1 and 2 separately.

All analysis result of Extension Study Period will be displayed by the following groups: CT-P10 maintenance (Group 1), Switched from Rituxan (Group 2), Rituxan maintenance (Group 3), Switched from MabThera (Group 4), and combined Switched from Rituxan and Switched from MabThera group.

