### 10.1. Serum concentrations

Pharmacokinetic samples will be listed for the safety population by each patient and sampling time point:

For Part 1, pharmacokinetic samples will be collected within 15 minutes prior to the beginning of the study drug infusion, within 15 minutes after the end of study drug infusion, and 1 hour ( $\pm 15$  minutes) after the end of study drug infusion on the day of each study drug infusion. For patients from Part 1 who receive only first course of treatment, additional samples will be collected after 24 hours ( $\pm 2$  hours) from the start of each study drug infusion in the first treatment course and on Week 1, 3, 4, 8, 12, 16 and 24, 15 samples in total. For patients from Part 1 who receive both

first and second courses of treatment, additional samples will be collected after 24 hours ( $\pm 2$  hours) from the start of each study drug infusion only in the first treatment course and on Week 1, 3, 4, 8, 12, 16, 48 and end of study (EOS; if patient withdraws prior to study completion), 21 samples in total.

For Part 2, pharmacokinetic samples will be collected within 15 minutes prior to the beginning of the study drug infusion, within 15 minutes after the end of study drug infusion, and 1 hour ( $\pm 15$  minutes) after the end of study drug infusion on the day of each study drug infusion. Additional samples will be collected on Week 24 (for patients who receive only first course of treatment) or Week 48 (for patients who receive both first and second courses of treatment) or EOS (for patients who receive both first and second courses of treatment and if patient withdraws prior to study completion).

Serum concentrations of rituximab will be summarized using descriptive statistics (consisting of n, mean, SD, CV, geometric mean, minimum, median and maximum) by part and treatment group at each scheduled collection visit and time point. Additionally, serum concentrations of rituximab for all antibody negative and positive subjects will be summarized by study part and treatment group at each scheduled collection visit and time point. In case of patients from Part 2, Combined Rituxan and MabThera group will be additionally displayed. Individual concentrations, scheduled and actual sample times will be presented in data listings by treatment group for the safety population.

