**Table 2: Pharmacokinetic Parameters for Rituximab**

Part 1 Primary Parameters (calculated over the first 24 weeks)	
AUC 0-last	Area under the concentration-time curve from time 0 to the last measurable concentration over both doses of the first course
AUC 0-∞	Area under the concentration-time curve from time 0 extrapolated to infinity over both doses of the first course

$C_{max}$	Observed maximum concentration after the second infusion
Part 1 Secondary Parameters (calculated over the first 24 weeks)	
$AUC_{0-day14}$	Area under the concentration-time curve from time 0 to Day 14 (calculated for both infusions)
$C_{max, 1}$	Observed maximum concentration following the first infusion of the first course
$C_{min}$	Predose concentration at Day 168 (Week 24)
$C_{trough}$	Predose concentration at Day 14 (Week 2) prior to the second infusion
$V_d$	Volume of distribution, calculated from the second dose of the first course as $V_d = \text{Dose}/AUC_{0-\infty} \times \lambda_z$ , where Dose is the combined total dose administered in Course 1 (i.e. Dose 1 + Dose 2)
CL	Total clearance, calculated from the second dose of the first course as $CL = \text{Dose}/AUC_{0-\infty}$ , where Dose is the combined total dose administered in Course 1 (i.e. Dose 1 + Dose 2)
$t_{1/2}$	Terminal phase elimination half-life, calculated from the second dose of the first course as $t_{1/2} = \ln(2)/\lambda_z$
$T_{max}$	Time to maximum serum concentration after both doses in the first course
Part 2 Secondary Parameters (up to Week 48 or over the first 24 weeks if second course of treatment is not administered)	
$T_{max}$	Time to maximum serum concentration in the first and second course
$C_{max}$	Observed maximum concentration after the second infusion in the first and second course
$C_{max, 1}$	Observed maximum concentration after the first infusion of the first and second course
$C_{min}$	Predose concentration at Day 168 (Week 24) and at Day 336 (Week 48)
$C_{trough}$	Predose concentration at Day 14 (Week 2 prior to second infusion) and at Day 182 (Week 26 prior to second infusion)

All AUC parameters will be calculated using the linear trapezoidal rule.

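### Part 2 first-course Tmax mixes patients with and without a 24-hour sample, so means can differ for MabThera, for combined reference versus CT-P10, and between courses even if the products are identical

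*SAP*

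**What the plan says.** **Parameters.** SAP section 10.2, Table 2, lists Tmax, Cmax and Cmax,1 as Part 2 secondary parameters for both courses. Tmax is "Time to maximum serum concentration in the first and second course" and Cmax is "Observed maximum concentration after the second infusion in the first and second course". Nothing in 10.2 limits the derivation to particular sampling times.

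**Sampling.** Every patient has predose, end-of-infusion and 1-hour samples at each infusion. For Part 1 patients, Protocol 12.1, Table 4, footnote 18 states that "additional samples will be collected after 24 hours (±2 hours) from the start of each study drug infusion in the first treatment course". SAP section 10.1 confirms the limit for patients who go on to a second course: the 24-hour samples are taken "from the start of each study drug infusion only in the first treatment course". For Part 2, SAP 10.1 says "Additional samples will be collected on Week 24 (for patients who receive only first course of treatment) or Week 48" (or the end-of-study visit), so no 24-hour sample is planned. Protocol Table 7 agrees: its Part 2 PK column shows none on Days 1 and 15, and neither part has one in course 2.

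**Who is pooled.** SAP section 5.4 states: "Population for Part 2 will include patients from Part 1". SAP section 4.1 assigns the patients enrolled after Part 1 to CT-P10 or Rituxan only, so every MabThera patient is a Part 1 patient.

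**Display.** SAP section 5.7 shows Main Study Period results for "CT-P10, Rituxan, MabThera, and combined Rituxan and MabThera group". SAP 10.2 summarises the PK parameters by part with n, mean, SD, CV, geometric mean, minimum, median and maximum.

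**The concern.** An observed maximum, and the time at which it occurs, depend on which samples were drawn. Without a 24-hour sample, Tmax falls at the end of infusion or one hour later. With one, a patient whose highest reading happens to be at 24 hours gets a Tmax near 24 h. In the Part 2 tables only Part 1 patients in course 1 can have such a value, and the share of these patients differs by column and by course. Randomisation does not balance this, because the imbalance comes from the sampling design. Analysing the two parts separately, as SAP 5.7 requires for PK, does not remove it either, because the Part 2 population contains Part 1.

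One Part 2 objective is to compare additional PK up to Week 48 with the reference products. A reader of these tables could take a sampling artefact for a product difference or for a change on repeat treatment.

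**Working it through.** **1. Reproduce the stated sample counts.** Protocol section 6.1 says: "The total number of samples for analysis of study drug concentration in Part 1 will be 21 samples per patient" with two courses, 15 with one, and 13 or 7 for Part 2.
- Part 1, first course to Day 112: 3 (Day 0) + 1 (Day 1) + 1 (Day 7) + 3 (Day 14) + 1 (Day 15) + 5 (Days 21, 28, 56, 84, 112) = 14. Adding 3 + 3 + 1 (Weeks 24, 26, 48) gives 21; adding 1 (Week 24) gives 15.
- Part 2: 3 + 3 = 6 in the first course. Adding 3 + 3 + 1 gives 13; adding 1 gives 7.

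All four figures agree. The remainder from Week 24 onwards is 7 in both schemes (21 − 14 and 13 − 6), so the schedules differ only in course 1.

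**2. Share of each column with a 24-hour candidate in course 1.** Planned numbers are 189/3 = 63 per arm in Part 1 and 172/2 = 86 per arm afterwards.
- CT-P10: 63/149 = 42.3%
- Rituxan: 63/149 = 42.3%
- MabThera: 63/63 = 100%
- Combined reference: 126/212 = 59.4%
- Course 2, every column: 0%

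Using the evaluable counts in the protocol synopsis changes little: 56/133 = 42.1% and 112/189 = 59.3%.

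**3. Time of the candidate samples.** Under the rate steps in Protocol 5.2, an uninterrupted 1000 mg first infusion takes 3.5 h for the first 700 mg plus 300/400 = 0.75 h, in total 4.25 h. The second takes 1.5 h for 300 mg plus 700/400 = 1.75 h, in total 3.25 h. Without a 24-hour sample, Tmax lies between about 4.25 and 5.25 h, or 3.25 and 4.25 h.

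**4. Size of the shift.** Mean Tmax in a column = T0 + share × (T1 − T0), where T0 is the mean without a 24-hour sample and T1 the mean with one. T0 and T1 come from a simulation of identical products with independent log-normal error on each reading. Two inputs are assumptions outside the documents: the fall from end of infusion to 24 hours, and the CV per reading. The lowest fall, 2.8%, follows from the protocol's half-life of about 20 days if decline is mono-exponential: 1 − 2^(−(19.75/24)/20) = 0.028. A distribution phase would make the fall larger.

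First infusion, mean Tmax in hours:

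| Fall by 24 h | CV | 24 h is highest | Course 2, all (T0) | CT-P10 = Rituxan | Combined reference | MabThera (T1) |
|---|---|---|---|---|---|---|
| 2.8% | 10% | 25.9% | 4.75 | 6.85 | 7.70 | 9.72 |
| 2.8% | 20% | 29.4% | 4.75 | 7.14 | 8.12 | 10.41 |
| 10% | 15% | 16.7% | 4.74 | 6.10 | 6.66 | 7.97 |
| 20% | 15% | 5.8% | 4.73 | 5.20 | 5.39 | 5.85 |
| 30% | 10% | 0.1% | 4.70 | 4.71 | 4.71 | 4.71 |
| 30% | 20% | 3.6% | 4.72 | 5.02 | 5.14 | 5.42 |

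Check of the first row: 4.75 + 0.423 × (9.72 − 4.75) = 6.85, and 4.75 + 0.594 × 4.97 = 7.70.

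Largest first-infusion differences (2.8% fall, 20% CV):
- combined reference minus CT-P10: 8.12 − 7.14 = 0.98 h
- MabThera minus CT-P10: 10.41 − 7.14 = 3.27 h
- CT-P10, course 1 minus course 2: 7.14 − 4.75 = 2.39 h

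For the second infusion the same setting gives about 1.0, 3.45 and 2.52 h. At the other end of the range all three are close to zero.

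**5. Cmax.** The largest ratios in the same range are 1.008 (combined reference to CT-P10), 1.028 (MabThera to CT-P10) and 1.020 (CT-P10, course 1 to course 2). Against the protocol's expected peak of about 400 µg/mL with SD 200, 2.8% is about 11 µg/mL.

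The simulation covers the 24-hour sample only. The Day 7 and Day 21 samples also exist only for Part 1 patients. If one were ever highest, it would add to the Tmax shift rather than offset it.

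**The case against.** No decision rests on these tables. Part 2 PK is secondary and descriptive, and the 80-125% criterion applies only to Part 1, where all patients share one schedule. The Part 1 tables already give a like-for-like first-course comparison of the three products, and SAP 10.1 summarises concentrations at each scheduled time point, where a 24-hour effect would be visible. The size depends on inputs that the documents do not give. The SAP also never says that a Part 1 patient's 24-hour sample feeds the Part 2 parameters.

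Most of this stands, and it keeps the point minor. On the last item, SAP 10.2 applies standard non-compartmental methods to each patient's concentration data and sets no limit. Use of all samples is therefore the natural reading, but it is an inference. The gap still needs closing, because two programmers could derive different values.

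A reader might also infer that CT-P10 is at odds with every reference column. The documents do not support that: CT-P10 and Rituxan have the same planned share, 63/149, so there is no expected artefact between those two.

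**Conclusion.** The point holds as a minor, design-made distortion of Part 2 Tmax. With identical products, the mean, SD and geometric mean can differ for MabThera and for combined reference against CT-P10, and between course 1 and course 2. The maximum is affected mainly between courses, since CT-P10 and MabThera each have 63 patients with a 24-hour candidate. Medians move little, because the 24-hour reading is highest in fewer than 30% of Part 1 patients in every case run.

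The size cannot be determined from the documents. Under the assumed ranges (fall 2.8-30%, CV 10-20%, uninterrupted infusions), and over both infusions, it runs from about zero to 1.0 h for combined reference minus CT-P10, about 3.4 h for MabThera minus CT-P10, and 2.5 h for CT-P10 course 1 minus course 2.

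It would be tempting to extend this to Cmax or to the PK similarity conclusion. Neither follows. The Cmax effect is under 1% for combined reference and under 3% for MabThera against CT-P10, and the Part 1 co-primary analysis does not mix schedules.

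**What to change.** In SAP section 10.2, Table 2, add that the Part 2 Tmax and, for consistency, Cmax and Cmax,1 are derived for all patients and both courses from the end-of-infusion and 1-hour samples only. Keep the full schedule for the Part 1 parameters. The share with a 24-hour candidate is then zero in every column and course, and the artefact disappears.

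Add a footnote that a Part 1 patient's Part 2 value may differ from the Part 1 value, and that a true 24-hour maximum appears only in the Part 1 tables.

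The cost is one SAP sentence, one filter in the derivation program and the footnote. No sampling changes. Because Protocol 7.1.3 does not restrict the samples, the rule should be recorded in the SAP as a change from the planned analysis, as Protocol 7.8 provides. Summarising first-course values separately for Part 1 and later patients would be an alternative, but it would still leave course 1 and course 2 on different schedules for Part 1 patients.

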### 10.3. Pharmacokinetic Statistical Analysis

In Part 1, the primary PK analysis will assess the similarity of CT-P10, Rituxan and MabThera in terms of  $AUC_{0-last}$ ,  $AUC_{0-\infty}$  and  $C_{max}$  over the first 24 weeks as co-primary PK endpoints.

ANCOVA will be performed for  $AUC_{0-last}$ ,  $AUC_{0-\infty}$  and  $C_{max}$  with treatment group as a fixed effect and country, gender, race, prior anti-TNF- $\alpha$  blocker status (intolerance case versus inadequate response) and RF or anti-CCP status (both positive versus both negative versus either

RF or anti-CCP negative) fitted as covariates. Clinically relevant variables at baseline are used as the covariates for adjusted means. If country is found to be unsuitable as a covariate due to the number of levels, then this may be pooled into a new variable, region (defined as either EU or Non-EU), for use in the statistical model. The  $AUC_{0-last}$ ,  $AUC_{0-\infty}$  and  $C_{max}$  will be natural log transformed prior to the analysis. Point estimates (geometric least squares means and ratios of geometric means) will be calculated by back-transforming the least squares means, and 90% CIs of the ratios (CT-P10 versus Rituxan, CT-P10 versus MabThera, and Rituxan versus MabThera) will be produced.

Similarity will be demonstrated if the 90% CI for the geometric mean ratio of CT-P10 to Rituxan and MabThera in  $AUC_{0-last}$ ,  $AUC_{0-\infty}$  and  $C_{max}$  is within the bounds of 80% and 125%.

When outliers occur at some time points, primary statistical analysis of PK parameters is carried out with data excluding observed outliers. However, a sensitivity analysis will also be performed with data including observed outliers. Additional ANCOVA for the PK primary endpoint will be conducted in patients whose ADA status result at Week 24 is “Negative” both including and excluding outliers. When there are Significant GCP non-compliance sites, an additional sensitivity analysis will be performed for PK primary endpoints.

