7.5 Sample Size Calculations

Part 1 of this study is powered to demonstrate PK similarity of CT-P10, Rituxan and MabThera in AUC_{0-last}, AUC_{0- ∞} and C_{max}. Similarity will be demonstrated if the 90%

confidence interval (CI) for the geometric mean ratio of CT-P10 to Rituxan and MabThera in AUC_{0-last} , $AUC_{0-\infty}$ and C_{max} is within the bounds of 80% and 125%.

In Part 1, based on overall 90% power, 2-sided alpha equal to 0.1, an interpatient coefficient of variation (CV) in AUC_{0-last} of 30%, and a true of geometric mean equal to 1, fifty patients are needed in each treatment group being compared (50 patients in the CT-P10 treatment group, 50 patients in the MabThera treatment group, and 50 patients in the Rituxan treatment group: 150 patients total). The statistical power of each comparison, CT-P10 versus MabThera, CT-P10 versus Rituxan and MabThera versus Rituxan is 96.5% to achieve overall 90% power accounting for multiplicity with type II error correction. Allowing for a drop-out rate of 20%, 189 patients will be randomly assigned into the study in a 1:1:1 allocation.

In Part 2, the sample size of 322 evaluable patients (133 patients in the CT-P10 group and 189 patients in the reference products group [Rituxan and MabThera groups]) leads to approximately 90% power for the demonstration of similarity based on a two-sided 90% CI for the difference of mean change of DAS28 score at Week 24 from baseline value between CT-P10 and reference products for an equivalence margin of ± 0.50 . In the sample size calculation, the common standard deviation of the mean change of DAS28 at Week 24 from baseline is assumed as 1.32 based on the CT-P10 1.1 study result for the therapeutic equivalence margin of ± 0.50 . Incorporating hypothesized drop-out rate of 10%, total sample size of 361 subjects (149 eligible patients in the CT-P10 and 212 eligible patients in the reference products group [Rituxan and MabThera groups], including up to 63 patients from each of the CT-P10, Rituxan and MabThera groups in Part 1) will be used in evaluation of efficacy endpoints.

In total, approximately 361 patients will be available for analysis (a total of approximately 149 patients for the CT-P10 group and 212 patients for the reference products group, including up to 63 patients from each treatment group in Part 1).

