7.8.1.1 Co-primary Pharmacokinetic Analysis

The primary PK analysis will assess the similarity of CT-P10, Rituxan and MabThera in terms of AUC_{0-last} (over both infusions of the first course of treatment, from time zero to the last measurable concentration), $AUC_{0-\infty}$ (over both infusions of the first course of treatment, from time zero to infinity) and C_{max} (after the second infusion of the first course of treatment) as co-primary PK endpoints.

The following PK parameters as co-primary PK endpoints will be calculated using noncompartmental methods:

- AUC_{0-last} will be calculated using trapezoidal rule. This will be calculated over both infusions in the first course of treatment.
- AUC_{0-∞} will be calculated using trapezoidal rule. This will be calculated over both infusions in the first course of treatment.
- C_{max} will be calculated after the second infusion in the first course of treatment.

In each part, for the calculation of PK parameters, all serum concentrations that are below the quantification limit (BQL) prior to the first measurable concentration will be set to zero. The BQL values after the first dose will be set equal to the lower limit of quantification. Actual sampling times, rather than scheduled sampling times, will be used in all computations of PK parameters.

- The primary PK parameter estimates will be analysed using an analysis of covariance (ANCOVA) with treatment as a fixed effect and country, gender, race, prior anti-TNFalpha (anti-TNF α) blocker status (inadequate response versus intolerant case), and RF or anti-CCP status (both positive versus both negative versus either RF or anti-CCP negative) fitted as covariates. If country is found to be unsuitable as a covariate due to the number of levels, then this may be pooled into a new variable, region defined in the SAP, for use as a covariate. Point estimates (geometric means and ratio of geometric means) will be calculated from back transforming the least squares means of the natural log-transformed values of AUC_{0-last}, AUC_{0- ∞} and C_{max}, and 90% CIs for the ratio of the geometric means of the 2 treatments (CT-P10 versus Rituxan, CT-P10 versus MabThera, and Rituxan versus MabThera) will also be produced. AUC_{0-last}, AUC_{0- ∞}, and C_{max} will be summarized by treatment. Summary statistics will include the mean, SD, median, minimum, maximum, geometric mean, and CV.

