### 5.2. Sample Size

For Part 1, 189 patients will be randomized in a 1:1:1 ratio to the CT-P10, Rituxan, and MabThera groups. Later, for Part 2, 172 patients will be allocated in a 1:1 ratio to the CT-P10 and Rituxan groups.

Part 1 of this study is powered to demonstrate PK similarity of CT-P10, Rituxan, and MabThera in  $AUC_{0-last}$ ,  $AUC_{0-\infty}$ , and  $C_{max}$ . Similarity will be demonstrated if the 90% confidence interval (CI) for the geometric mean ratio of CT-P10 to Rituxan and MabThera in  $AUC_{0-last}$ ,  $AUC_{0-\infty}$ , and  $C_{max}$  is within the bounds of 80% and 125%.

In Part 1, based on overall 90% power, Two one-sided alpha equal to 0.05, an interpatient CV in  $AUC_{0-last}$  of 30%, and a true of geometric mean equal to 1, fifty patients are needed in each treatment group being compared (50 patients in the CT-P10 treatment group, 50 patients in the MabThera treatment group, and 50 patients in the Rituxan treatment group: 150 patients total). The statistical power of each comparison, CT-P10 versus MabThera, CT-P10 versus Rituxan,

and MabThera versus Rituxan is 96.5% to achieve overall 90% power accounting for multiplicity with type II error correction. Allowing for a drop-out rate of 20%, 189 patients will be randomly assigned into the study in a 1:1:1 allocation.

In Part 2, the sample size of 322 evaluable patients (133 patients in the CT-P10 group and 189 patients in the reference products group [Rituxan and MabThera groups]) leads to approximately 90% power for the demonstration of similarity based on a two-sided 90% CI for the difference of mean change of DAS28 (CRP) score at Week 24 from baseline value between CT-P10 and reference products for an equivalence margin of  $\pm 0.50$ . In this sample size calculation, the common standard deviation of the mean change of DAS28 at Week 24 from baseline is assumed as 1.32 based on the CT-P10 1.1 study result for the therapeutic equivalence margin of  $\pm 0.50$ . Incorporating hypothesized drop-out rate of 10%, total sample size of 361 subjects (149 eligible patients in the CT-P10 and 212 eligible patients in the reference products group, including up to 63 patients from each of the CT-P10, Rituxan, and MabThera groups in Part 1) will be used in evaluation of efficacy endpoints.

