## **7. Demographics, Baseline Characteristics, and Background Characteristics**

### **7.1. Demographics**

The following demographic measures will be tabulated for the all-randomized population and all-randomized population – Extension Study Period subset by treatment group and part: age (years); gender (male, female); female fertility status (Pre-menarche, sterile, post-menopausal, potentially able to bear children); race (white, black, Asian, other, not allowed by investigator country regulations); height (cm) and weight (kg) as recorded at the screening visit; Body-Mass Index (BMI) ( $\text{kg}/\text{m}^2$ ); country; region (EU, non-EU).

Age will be automatically calculated in the eCRF system based on the date of the informed consent visit and the date of birth provided. Patients from some countries may have the information of the year of birth only. When date and month are missing for date of birth, age will be derived using the year of birth and the year of informed consent only.

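### The co-primary PK model has no body-size term although the dose is fixed and weight is measured before dosing: an optional, conditional gain in precision, not an error

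*SAP*

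**What the plan says.** Dosing is flat: Protocol 5.2 gives each course as two infusions of 1000 mg, with no scaling to body size.

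Weight is available. In the main schedule of events (Protocol 12.1, Table 4) it is measured with the vital signs at Screening and before the infusion on Day 0. SAP 7.1 tabulates "height (cm) and weight (kg) as recorded at the screening visit".

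The co-primary PK model does not use it. Protocol 7.8.1.1 specifies an ANCOVA "with treatment as a fixed effect and country, gender, race", followed by prior anti-TNF status and RF/anti-CCP status. SAP 10.3 repeats the list, allows EU/non-EU region in place of country, and comments that "Clinically relevant variables at baseline are used as the covariates for adjusted means". The further PK analyses in SAP 10.3 cover outliers, ADA-negative patients and GCP non-compliant sites; none adds weight.

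Protocol 7.5 sizes Part 1 "based on overall 90% power, 2-sided alpha equal to 0.1", with a CV for AUC0-last of 30% and "a true of geometric mean equal to 1", meaning a true geometric mean ratio of 1. It says that each pairwise power "is 96.5% to achieve overall 90% power accounting for multiplicity with type II error correction". SAP 5.2 words the alpha as "Two one-sided alpha equal to 0.05", which is the same test.

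**The concern.** After a fixed dose, body size is a natural candidate predictor of exposure, and it is the obvious one missing from the model. Three of the five covariates are the randomisation strata (SAP 5.3), and the same core list serves the efficacy and PD models (SAP 11.2, 12.2). The SAP gives no sign that the list was chosen with exposure in mind and no reason for leaving weight out.

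Precision matters because several 90% intervals must all lie within 80–125%. Protocol 7.8.1.1 requires all three pairs on all three parameters, which is nine intervals. SAP 10.3 and Protocol 7.5 word the rule as CT-P10 against each reference, which is six. Under either count, a covariate that predicts exposure would narrow every interval and would adjust each ratio for any chance difference in weight between arms of about 50.

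**Working it through.** **Inputs from the documents.** CV 30%; true ratio 1; limits ±ln 1.25 = ±0.2231; one-sided alpha 0.05; 50 evaluable per group; 20% drop-out (Protocol 7.5, SAP 5.2).

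**Assumed.** R², the share of the variance left after the existing covariates that weight explains. The documents give no value, so a range including zero is shown. CVs of 35% and 40% are also assumptions.

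**Step 1: the plan's own figure.**
- Log-scale SD = √ln(1 + 0.30²) = 0.2936.
- SE of a difference = 0.2936 × √(2/50) = 0.0587.
- Normal approximation to power: 2Φ(0.2231/0.0587 − 1.645) − 1 = 96.9%.
- Exact two one-sided tests power, integrating over the distribution of the residual variance with 98 df: 96.7%, against 96.5% stated.
- Overall for three pairs: 1 − 3(1 − 0.9668) = 90.0%, or 0.9668³ = 90.4%, against 90% stated.
- Drop-out: 50/0.8 = 62.5, so 63 per group and 189 in total, as stated.

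The design reproduces with no credit for any covariate.

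**Step 2: effect of a weight term.** The SD is multiplied by √(1 − R²) and one df is lost. The SE reduction is 1 − √(1 − R²): 0 at R² = 0, 2.5% at 0.05, 5.1% at 0.10 and 10.6% at 0.20. Exact power per comparison (%), 50 per group, true ratio 1:

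| CV | R² = 0 | 0.05 | 0.10 | 0.20 |
|---|---|---|---|---|
| 30% | 96.7 | 97.4 | 98.0 | 99.0 |
| 35% | 89.4 | 91.1 | 92.7 | 95.4 |
| 40% | 78.2 | 80.8 | 83.4 | 88.4 |

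At CV 30% the upper 90% confidence limit, for an observed ratio of 1, moves from 1.102 to 1.091 at R² = 0.20.

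**Step 3: credit to the existing covariates.** The table applies the whole CV as residual variability. If the five existing covariates already explain a share E of the variance (assumed), the SD is also multiplied by √(1 − E). At CV 30%:

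| E | without weight | weight R² = 0.05 | weight R² = 0.20 |
|---|---|---|---|
| 0 | 96.7 | 97.4 | 99.0 |
| 10% | 98.0 | 98.5 | 99.5 |
| 20% | 99.0 | 99.3 | 99.8 |

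The gain shrinks from 0.7–2.3 points to 0.5–1.5 or 0.3–0.8 points.

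**Step 4: is a CV above 30% relevant?** The 30% is stated for AUC0-last only; no CV is given for AUC0-∞ or Cmax. Protocol 1 expects peak concentrations near 400 µg/mL with an SD of 200, and 200/400 = 50%. That is a background expectation and not a design input, but it is why the higher-CV rows are shown.

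**The case against.** The strongest reply is that nothing in the plan is wrong. The model contains every stratification factor plus gender and race, the stated power is reached without weight, and the SAP's remark about clinically relevant variables describes the list without promising every plausible predictor. All of that stands.

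Three stronger readings are tempting, and the documents do not support them.

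- **That weight is known to drive exposure here, so the gain is certain.** No passage relates weight to rituximab exposure. A fixed dose alone does not show that weight explains variance beyond gender, race and country, which may already carry part of any body-size effect. At R² = 0 the gain is nil.
- **That Part 1 is underpowered.** By its own inputs it is not. The large gains appear only at CVs above the planning value.
- **That chance imbalance in weight biases the comparison.** Under randomisation it does not. It is part of the random error that the unadjusted interval already covers, and should not be counted as a second harm beside residual variance.

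Timing is also a fair objection. This SAP serves the final analysis (SAP 2), while the sponsor is unblinded for the Week 24 PK and efficacy report (SAP 5.3). A primary model altered after that point would be post hoc.

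What survives is narrower: a pre-dose measurement with an evident possible link to exposure is left out of the model and of every sensitivity analysis, without a reason, when including it costs almost nothing.

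**Conclusion.** The point holds as a minor improvement. At the planned CV of 30%, adding weight would raise power per comparison by between nothing and about 2.3 points, less if the existing covariates already reduce the variance. At a CV of 40% the gain would be between nothing and about 10.2 points (78.2% to 88.4%). These figures rest on an assumed R² of 0 to 0.20, a true ratio of 1 and 50 evaluable patients per arm. The value is mainly insurance: it counts most if variability exceeds the planning value, and it would show whether the ratios are stable to adjustment for body size.

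**What to change.** Add log baseline body weight as a continuous covariate in the SAP 10.3 ANCOVA for AUC0-last, AUC0-∞ and Cmax. State which measurement is used; the baseline rule in SAP 5.5 points to the last value before the first infusion. Because Protocol 7.8.1.1 fixes the covariate list, record this in the SAP as a change from the protocol before unblinding, as Protocol 7.8 requires.

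If the Week 24 PK results have already been unblinded, keep the protocol model as primary and report the weight-adjusted model beside it, labelled as a sensitivity analysis added after unblinding.

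The cost is one model term on data already collected, about one of 98 degrees of freedom in each pairwise comparison, and one documented change to the covariate list.
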